### 392 1.11.1 Clinic eligibility criteria

393 We selected these clinics by working with our advisory board to establish criteria for clinic participation.

- 394 Below is a list of these criteria. These criteria are listed below.
- 395

Clinic Criteria	Description
Clinic site size	A clinic site must have 450+ patients aged 50 - 74
Number of clinic sites in organization	Clinic organization must have at least 2 sites that meet size requirement.
FOBT/FIT	Clinic organization must use the same screening method in its intervention and usual care clinics.
Colonoscopy capacity	Clinic must have sufficient capacity to perform colonoscopies for patients who screen positive on FOBT/FIT.
Lab interface/ capacity	Clinic sites must have direct electronic interface with lab that processes FOBT/FITs; lab must have sufficient capacity to process additional tests.
Randomization	Clinics must agree to randomize their clinics; each organization will be assigned at least one intervention and one usual care site.
Testing the uninsured	Clinic organization must have a plan for screening for uninsured patients.
Research requirements	Clinic organizations must consent to leadership requirements (clinic interviews, data validation, advisory board involvement, interpretation of findings)
Prioritization/ willingness	Clinic leadership must prioritize project and set improvement targets.
Human Subjects requirements	Clinic organization must agree to cede to KP NW IRB.
Federal Wide Assurance	Clinic organizations must maintain active FWAs

#### 397 1.11.2 Clinic Recruitment Procedures

OCHIN and CHR staff reviewed lists of possible health centers and determined which were eligible. Health Center
 representatives were sent an email from OCHIN introducing the project and obtaining permission to provide
 contact information to CHR investigators. All health centers agreed. Health Center representatives were then
 contacted by [name], Community Research Liaison, who organized in-person or WebEx meeting with
 leadership teams. These meetings lasted 1.5 hours. [name] provided the following clinic recruitment

- 403 materials to attendees during these meetings:
- Introduction to STOP CRC (document and PowerPoint)
- 405 Scope of work
- 406 Budget templates
- Draft letter of support
- 408 Sample staffing plan

Health Center representatives were asked to respond with their interest in participating in the STOP CRC projectby September 1, 2013.

411

#### 412 **1.12** Selection of Eligible Patients

413 The main eligibility criteria for STOP CRC are screening criteria as adopted by the National Quality Forum (NQF).

Patients must be 50-74 years old, an active patient identified by a prior visit, without screening or conditions that

415 would make them poor candidates for screening. Below is a list of the inclusion and exclusion criteria for the 416 project.

Inclusion and Exclusion Criteria for STOP CRC Patient Participants	Time	Temporary/Permanent**
Inclusions		
Aged 50-74	Current	Temporary
Have at least 1 visit in past 12 months	Past 12 months	Temporary
Have viable address	Current	Temporary
Exclusions – CRC screening history		
Colonoscopy Complete	Past 9 years	Temporary
Colonoscopy Referral	Past 1 year	Temporary
Gastroenterology Referral	Past 1 year	Temporary
FIT (or FOBT) Orders	Past 11 months	Temporary
Flex sigmoidoscopy Referral	Past 1 year	Temporary
Flex sigmoidoscopy Complete	Past 4 years	Temporary
Exclusions – Colorectal disease		
Prior dx of colorectal cancer	Ever	Permanent
Prior dx of total colectomy	Ever	Permanent
Ulcerative colitis and Inflammatory Colitis	Ever	Permanent

History of high risk polyps –	Ever	Permanent
Exclusions: co-morbid conditions		
History of renal failure/ESRD	Ever	Permanent
Living in nursing home or assisted living	Past 1 year	Temporary
Hospice Program	Ever	Permanent

\*Additional local codes should be included in procedures list if available.

419 \*\*Temporary means that status can change during observation period.

420

421 The tables below list the codes that were used to identify colonoscopy orders, results and GI referrals, FIT/FOBT orders, flexible sigmoidoscopy referrals and completions, colorectal disease, and co-morbid

422 conditions.

423

424

#### Codes to Identify Colonoscopy Orders or Results and GI Referral

Description	ICD9*/CPT Codes	HCPCS**
Colonoscopy Orders/Referral/Results	44388-44394, 44397, 45355, 45378-45387, 45391, 45392	G0105, G0121
Virtual Colonoscopy Referral	0066T,0067T 74261-74263	
GI Referral		Referral Code indicating GI or colonoscopy referral or 9110 or 9140 for colonoscopy referral

425

\*International Classification of Disease, Version 9

426 \*\* Healthcare Common Procedure Coding System

427

Codes to Identify FIT/FOBT orders		
Description	ICD9*/CPT Codes	HCPCS**
FIT/FOBT orders	82270, 82274	G0107, G0328, G0394

428 429

\*International Classification of Disease, Version 9 \*\* Healthcare Common Procedure Coding System

430

Codes to Identify Flexible Sigmoidoscopy Referral and Completion		
Description ICD9*/CPT Codes HCPCS**		
Flex sigmoidoscopy Referral	45330, 45331, 45332, 45333, 45334, 43335, 45337, 45338, 45339, 45340, 45341, 45342, 45345	G0104
Flex sigmoidoscopy completion		

431

\*International Classification of Disease, Version 9 432 \*\* Healthcare Common Procedure Coding System

433

**Codes to Identify Colorectal Disease** 

Description	ICD9*/CPT Codes	HCPCS**
Prior dx of colorectal cancer	153, 154.0, 154.1, 197.5	V10.0
Prior dx of total colectomy	44150-44153, 44155-44158, 44210- 44212	
Ulcerative colitis or inflammatory colitis	555, 556	
History of high risk polyps	211.3, 199.1	

\*International Classification of Disease, Version 9 \*\* Healthcare Common Procedure Coding System

436

Codes to Identify Co-morbid Conditions		
Description	ICD9*	HCPCS**
History of renal failure / ESRD	585.5, 585.6 and 586	Referral to dialysis
Living in nursing home / assisted living		Referral to nursing home
Under hospice care		Referral to hospice

437 \*International Classification of Disease, Version 9

438 \*\* Healthcare Common Procedure Coding System

439

### 440 **1.13** Enrollment Procedures and Participant Identification

OCHIN programmers will develop an algorithm for using the EHR to automatically identify eligible patients,
which will be updated regularly, so that the new data such as FOBT completion can be applied to those patients
who are eligible to receive the automated intervention at each clinic. The electronic tools will automatically
provide a list of eligible patients in the Reporting Workbench tool in EPIC. Clinics will review the patient list prior

- to mailing the introductory letter to assess whether the patient is appropriate for screening.
- 446

### 447 **1.14** Intervention Delivery and Core Components

The intervention components are a mailed fecal test and an improvement cycle (e.g., a PDSA cycle). Each potential participant will be sent an introductory letter introducing the study, asking them to call if they have prior screening or clinical concerns. The letter will contain a toll-free telephone number that the participant can use to call the clinic if he or she does not want any further contact from the study. A patient can also choose another type of screening method, such as colonoscopy. Depending on the clinic's preference, the mailings may take place every month based on the birthday month of the patient, or less frequently depending on the clinic flow.

- 455
- Clinic staff will log whether a patient declines to participate in the study and declination rates will
   be monitored by the study team.
- One month after the mailing of the introductory letter, those patients not reporting being current
   for screening, who have a viable address and have not called to opt out of the program (because of
   prior screening or other reasons) will be mailed a FIT kit;
- One month after the mailing of the FIT kit, those not reported as completing the kit will be mailed a reminder postcard.

- Four to 6 months after the mailing of the FIT kit, an improvement cycle will be facilitated with the clinic; this will identify strategies to further enhance the reach or effectiveness of the program.
- Phase 1 of the study developed the participant intervention materials, which consist of the following (seeAppendix D for samples):
- STOP CRC introductory letter (in English and Spanish)
  - STOP CRC wordless FIT kit instruction

STOP CRC reminder postcard

469

2

[figure not shown]
470 471

468

Statistical Analysis Plan

#### 472 2.1 Study Design

473 STOP CRC is a two-arm cluster randomized design with clinic as the unit of randomization and analysis. The 474 analysis plan is based on an adapted consort diagram, see **Figure 4**:

\*adapted from extended CONSORT diagram (Kessler 2011)

### 476 **2.2. Randomization**

477 Based on simulation work conducted by the Collaboratory's Biostatistics Core, we abandoned our original

478 plans to conduct a constrained randomization and instead opted for a simple stratified randomization

based on Health Center. Within each of these administrative units, the randomization was blocked to

480 assure maximum possible balance of intervention and control clinics. Having created the basic

- randomization scheme with two groups (A and B), the assignment of the groups to intervention and control
- 482 conditions was performed randomly on a conference call with all health center representatives on February
- 4th, 2014 to assure maximum transparency of the process to our participating sites. The randomization
   process relied on an electronic dice that was rolled by a member of the advisory board.
- 485

## 486 **2.3 Study Outcomes**

487 The original UH3 protocol stated that the study population would be accrued over the 12 months following

randomization (February 4, 2014–February 3, 2015) and then be followed for 12 months after that to assess

489 the study outcome. However due to the decision to roll out the intervention to control clinics in August of

2015, we truncated the follow up window for all individuals, intervention and control, as of this date. In
addition, delays in intervention startup required us to reformulate some of our secondary outcomes. The

- 491 addition, delays in intervention startup required us to reformulate some of our second.
- 492 revised is a statement of our current primary and secondary outcomes.

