## 493 2.3.1 Primary Outcome Variable

Our primary outcome is the completion of fecal testing within the earlier of (a) 12 months from study
accrual or (b) August 3, 2015 (when study tools were made available to usual care clinics). As our primary
interest was on clinic level return rates, however, these individual responses were weighted by 1/(clinic
size) so that each clinic's data was weighted equally (see section 2.4.1).

498

510

511

512

513

514

515

516

517

To assure maximum comparability of the intervention and control samples, all participants were accrued in the same manner. For control clinics we thus looked for the first date that a participant would have been eligible to receive the intervention had it been turned on for that site. It follows that both the distribution of accrual times as well as the distribution of follow up times should be comparable for participants in the two groups.

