## 505 2.3.2 Secondary Outcomes

[figure not shown]
- 506 Our secondary outcomes are provided below:
- For participants who received a FIT kit, the probability of returning it within 3, 6, 9 and 12 months of its being sent as well as time to FIT/FOBT return
   Receipt of any CRC screening (fecal test, sigmoidoscopy or colonoscopy) during the follow-
  - NQF score (proportion of those age 50-74 with a colonoscopy within 10 years, flexible
  - sigmoidoscopy within 5 years, and FOBT/FIT within 1 year) as assessed relative to the oneyear pre and each of the first two years post randomization
    - Presence of a positive FIT/FOBT among those who return a FIT kit
    - Referral for a colonoscopy among those with a positive FIT/FOBT
    - Completion of a colonoscopy following a positive FIT/FOBT

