### 637 Secondary Analyses

638 We used the same analytic approach for the secondary outcome of any CRC screening. For both FIT

- 639 completion and any CRC screening, additional models were fit using interaction terms to test the extent to
- which the intervention effect differed across Health Centers. The interactions were treated as fixed effectsin these models.
- 642

643 The analysis of our other secondary outcomes will be more descriptive in nature. Regarding the proportion 644 of returned FOBT/FIT kits that turn out positive, while we anticipate a sizeable number of returned 645 FOBT/FIT kits for each of the intervention clinic (typically in excess of 150), the numbers will be much 646 smaller for control clinics (for many of the smaller clinics less than 20) and hence much less precisely 647 measured. The situation is only compounded for the secondary outcomes of referral for a positive FIT and 648 completion of a colonoscopy following referral, since they are further limited to FOBT/FIT kits that are 649 returned and are positive. Hence, for all these outcomes, the focus will be more on the experience of the 650 intervention clinics than formal comparisons between intervention and control clinics, though we will look 651 at this latter question to the extent we are able. Ultimately, we wish to know the extent to which the 652 clinics are able to maintain the program and the impact it may have on their operations, and hope that this 653 information will help to shed light on this issue.

654

For the NQF scores, the data can be interpreted as coming from a step wedge design. In the year prior to
randomization all clinics were following usual care. In the first-year post randomization the intervention
clinics were using the intervention and the control clinics still usual care. In the second-year post
intervention all clinics were using the intervention. In each case we have a single observation per clinic.

659 We will use a random effects model to assess intervention effects while adjusting for within clinic

- 660 clustering. The model will allow for period effects and will also estimate separate effects for the first and
- 661 second year of intervention rollout.
- 662
- 663 Sensitivity Analyses

664 Sensitivity analysis will include GEE models without weighting, GEE models that also adjust for insurance 665 status, random effects models, and models excluding the two clinics (one intervention and one control)

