- 666 affiliated with an academic medical center (these clinics did not have shared governance and did not use 667 the same FIT kit throughout the intervention).
- 668

669 Finally, while our primary analysis will include all individuals accrued after EHR tools were provided to

670 clinics on February 4, 2014, no clinic began printing letters until at least June of 2014; some did not begin

671 until spring of 2015. To account for this implementation delay, we will repeat the above analyses for FIT

- 672 completion and "any CRC screening" using a lagged dataset that only included individuals accrued between
- 573 June 4, 2014 and February 3, 2015. As with the primary dataset, outcomes for this lagged dataset will be
- assessed through August 3, 2015, after which materials were made available to usual care clinics.
- 675

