Unusable kit	0	(0.0)	0	(0.0)	0	(0.0)	0	(0.0)	0	(0.0)	0	(0.0)
Colonoscopy/ Flex Sig referrals as follow-up to positive FITS (within 6 months)												
Colonoscopies/ Flex Sig completed (within 6 months)												
TOTAL FIT/FOBT Return Rate in past 12 months												
TOTAL Colonoscopy Rate in past 12 months												

\*Medically ineligible include conditions that prompt direct referral to GI, such as ulcerative colitis, Crohn's disease, and immediate family history of colorectal cancer; patient under hospice care, or otherwise medically ineligible for fecal testing.

\*% reflected is of patients eligible after

exclusions.

1072 1073

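### The August 2015 cut-off leaves many patients with too little follow-up for referral and colonoscopy after a positive FIT, and section 2.3.2 sets no window for these two outcomes

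*Protocol*

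**What the plan says.** **Follow-up.** Section 2.3 stands over both the primary and the secondary outcomes. The earlier plan was to accrue over the year after "randomization (February 4, 2014–February 3, 2015) and then be followed for 12 months after that to assess" the outcome. Because the programme was to be released to control clinics in August 2015, "we truncated the follow up window for all individuals, intervention and control, as of this date". The primary outcome (2.3.1) stops at the earlier of 12 months from accrual or "August 3, 2015 (when study tools were made available to usual care clinics"). Section 2.4.1 uses the same date for FIT completion and any CRC screening in the lagged dataset.

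**The two outcomes.** Section 2.3.2 lists referral for colonoscopy among those with a positive test, and "Completion of a colonoscopy following a positive FIT/FOBT". Neither carries a time window or a cut-off of its own. The sample Final Disposition report (4.2.3) has a row "Colonoscopies/ Flex Sig completed (within 6 months") and a referral row with the same 6 months; both rows are blank.

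**Timing of mailings.** Section 2.4.1 says that "no clinic began printing letters until at least June of 2014; some did not begin" until spring 2015. Section 1.7 puts the kit 2 weeks to 1 month after the letter.

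**Use of the outcomes.** Section 2.4.1 treats them as descriptive: "Hence, for all these outcomes, the focus will be more on the experience of the" intervention clinics than on formal comparison of arms. It hopes they will help show whether clinics can maintain the programme.

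**The concern.** These two outcomes show whether a positive test found by the programme is worked up. Their clock should start at the positive result, but the stated truncation ends observation on a calendar date. Observation time after a positive therefore depends on when the clinic began mailing: long in a clinic that began in June 2014, very short in one that began in spring 2015. No section says how a positive with a short window is to be counted.

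If completion is reported as a plain proportion of all positives, a patient awaiting colonoscopy on 3 August 2015 is indistinguishable from one who was never worked up. The figure would be too low overall, and clinics would be ranked partly by start date. It would be a poor guide to the question that 2.4.1 wants it to inform.

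**Working it through.** The protocol gives no completion figure to reproduce. The check is calendar arithmetic, followed by an illustration.

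**1. Latest positive with a full window** (cut-off from 2.3.1, window from 4.2.3)

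- 3 August 2015 minus 6 months = 3 February 2015, which is 181 days earlier.
- This is also the last accrual date in 2.3. A patient accrued that day has 181 days in all for letter, kit, return, result, referral and colonoscopy.

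**2. Clinics that first printed letters in spring 2015** (taken as 1 March to 31 May; kit lag of 14 to 31 days from 1.7)

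| First letter | Days from letter to cut-off | Days from kit to cut-off |
|---|---|---|
| 1 March 2015 | 155 | 155 − 31 = 124 to 155 − 14 = 141 |
| 31 May 2015 | 64 | 64 − 31 = 33 to 64 − 14 = 50 |

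Every entry is below 181 before any time for return and result is deducted. No mailed-kit positive in these clinics can have 6 months. This step needs no assumption beyond the months taken as spring.

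**3. Illustrative share of mailed-kit positives with a short window**

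Assumptions, none of them in the protocol except the kit lag: accrual uniform over 4 February 2014 to 3 February 2015; letter sent 0 to 90 days (uniform) after the later of accrual and clinic start; kit 14 or 31 days after the letter; exponential return lag with mean 14 or 60 days. Share s of positives seen by the end of follow-up that have fewer than 181 days left:

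| Clinic starts letters | Cut-off 3 August 2015 only | 12-month limit from accrual also applied |
|---|---|---|
| June 2014 | 20–37% | 25–53% |
| October 2014 | 22–60% | 56–80% |
| Spring 2015 | 100% | 100% |

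**4. What this does to a plain proportion**

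Let F(t) be the true proportion worked up within t days of a positive, taken as the same for early and late positives. The reported proportion is

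R = (1 − s) × F(181) + s × mean of F(d) over the short windows, with d < 181.

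Since 0 ≤ F(d) ≤ F(181), the ratio R / F(181) lies between 1 − s and 1. With the 3 August cut-off alone:

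- June 2014 start: the lower bound is 1 − 0.37 = 0.63 to 1 − 0.20 = 0.80.
- October 2014 start: the lower bound is 1 − 0.60 = 0.40 to 1 − 0.22 = 0.78.
- Spring 2015 start: s = 1, so the lower bound is 0.

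Where R falls between its bound and 1 depends on the time-to-colonoscopy distribution, which the protocol does not give. The direction does not: R cannot exceed F(181), and the bound is loosest in late-starting clinics.

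**5. Does the reason for truncating apply?**

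The cut-off exists because usual care clinics received the tools (2.3.1). That protects the comparison of FIT completion between arms. Intervention clinics already had the tools, and the clock for these outcomes starts at a positive already obtained. The roll-out therefore gives no reason to stop observing work-up in the clinics on which 2.4.1 says these outcomes focus.

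**The case against.** There is a serious case on the other side.

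- **The 6 months is not the outcome definition.** It appears only in an appendix template filled with placeholder counts. That template also reports kit return at 10 months, which is not among the 3, 6, 9 and 12 months of 2.3.2. A reader might infer that the protocol defines completion within 6 months and then breaks its own rule. It does not: 2.3.2 has no window. The gap remains, because an outcome with no window and a calendar cut-off has follow-up that varies between patients whatever window is later chosen.
- **The cut-off may not have been meant for these outcomes.** The exact date is written only for the primary outcome and, in the lagged dataset, for FIT completion and any CRC screening. The NQF score runs through the second year after randomization. But the statement in 2.3 covers all individuals, introduces the secondary outcomes too, and exempts neither of these.
- **No counting rule is stated.** A reader might infer that the plan counts unfinished work-ups as missed follow-up. The protocol does not say so; this follows only if a plain proportion over all positives is taken. Nor does it provide for censoring or a restricted denominator.
- **Late-starting clinics have other positives.** The outcome covers any positive FIT/FOBT, and usual-care tests from February 2014 on could have full windows. It would be wrong to say that no positive in such a clinic can be followed for 6 months; this holds for mailed kits only. The shares in step 3 leave out the other positives and so tend to overstate the problem.
- **The outcomes are descriptive.** No test, power statement or primary conclusion rests on them, and positives up to 3 February 2015 can have a full window under the calendar cut-off. This limits the importance of the point but does not remove the unequal follow-up.

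**Conclusion.** The point holds in a limited form and should be acted on. Applied as written, the August 2015 truncation gives positives unequal and often short observation. None dated after 3 February 2015 can be followed for 6 months, nor can any mailed-kit positive in a clinic that first printed letters in spring 2015. Those two statements rest on the protocol's dates and the 6 months of 4.2.3.

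A plain proportion would be biased low, most in late-starting clinics. That further step assumes that the truncation reaches these outcomes and that no allowance is made for incomplete windows. The size cannot be fixed from the protocol. The illustrative shares with a short window, from about one fifth to all mailed-kit positives depending on start date, show only that it need not be small.

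The consequence is confined to two descriptive secondary outcomes. The primary outcome is unaffected, and nothing here questions the truncation for FIT completion or any CRC screening.

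**What to change.** **Preferred.** In 2.3 and 2.3.2, exempt referral and colonoscopy completion after a positive FIT/FOBT from the August 2015 truncation. For each positive dated on or before 3 August 2015, ascertain both for a fixed window from the result, using the 6 months already in 4.2.3 so that definition and report agree. This is a measurement window, not a statement of when work-up should occur. The last extraction falls about 3 February 2016. At the same time, reconcile the denominator for completion: 2.3.2 counts from the positive test, whereas 2.4.1 speaks of completion after referral.

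**If no later data can be obtained.** Either restrict the denominator to positives with a full window, which drops every mailed-kit positive from the spring 2015 clinics, or give a time-to-event estimate censored at the end of follow-up. Report the number of positives with incomplete windows by clinic.

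**Unchanged.** Keep the truncation for FIT completion and any CRC screening. In any comparison with control clinics on the two exempted outcomes, note that work-up after 3 August 2015 took place once the tools had been released there.

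**Cost.** One later EHR extraction limited to patients with a positive test, and a later data lock for two descriptive outcomes. Two years after the 4 February 2014 randomization is also about 3 February 2016, so the year-2 NQF score already needs colonoscopy data to about that date; the main addition is referrals.
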